The overall goal of Outside In's HCV treatment program is to improve the care of its patients suffering from chronic Hepatitis C virus and to standardize the screening, diagnosis, work-up, and treatment of this condition throughout Outside In. Patient-centered design to increase success in the recruitment and treatment of actively using, homeless or high-risk patients is at the core of the creation of this program. Essential parts of Outside In's program include recruitment and referral from Outside In's syringe exchange program as well as referral by the primary care provider (PCP) from within our homeless health services, initial office visit and assessment with an Outside In HCV provider, tailored weekly or bi-weekly medication dispensing, bi-weekly clinical pharmacist visits, monthly lab monitoring, and optional participation in HCV harm-reduction/ re-infection prevention education sessions. All of these services are provided at Outside In, the patients' primary care medical home.

Old Town Clinic

Old Town Clinic (OTC) is part of Central City Concern (CCC), a multi-faceted social service agency whose mission is to provide comprehensive solutions to ending homelessness and achieving self-sufficiency. Old Town Clinic is a Federally Qualified Health Center and a Healthcare for the Homeless clinic located in downtown Portland, Oregon. This is an integrated, multi-disciplinary primary care clinic serving over 4,900 homeless and low-income adults living with a broad range of social, behavioral, and medical conditions. More than 70% of OTC patients are homeless and 99% are at or below 100% of the federal poverty level. The population of Old Town Clinic has a high prevalence of chronic hepatitis C infection. In addition, the patient population has a high prevalence of severe and persistent mental illness, addiction, and chronic medical illness. For these reasons, many of its patients are not currently candidates for chronic hepatitis C treatment, and even if they are candidates, the barriers to receiving treatment are insurmountable. The consequences of which are not insignificant as 24% of its patients are known to suffer from chronic hepatitis C, and among patients with the most advanced illness, the known prevalence is 56%. The morbidity and mortality of chronic hepatitis C infection as well as the costs to the healthcare system have been well described.

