OHSU (Retrospective). The OHSU principle investigator, or IRB approved surrogate, will review the hepatology clinic Electronic Medical Record for patients treated for hepatitis C with Zepatier and select subjects in a retrospective, sequential fashion, starting at the time of closure of enrollment at the two prospective sites.

f. Consent Process

The consent coordinator will obtain consent during the intake appointment, after the initial screening process as detailed below. The consent coordinator will be an IRB-approved, OHSU affiliated employee of the study site, with 50% of their FTE covered by grant funding. This will occur in person, in a confidential clinic exam room, with ample time for questions and clarifications. The consent form will also be provided prior to the appointment so subjects have time to read over it and highlight any questions or concerns they may have. Subjects with low self-reported reading literacy will have the consent form read to them with a teach-back to confirm understanding. While all study coordinators will be employees of their parent organizations and will have access to the medical record, they will not be medical providers with a long standing relationships with the subjects to minimize potential for coercion and conflicts of interest.

For the purposes of this pilot study, only subjects who identify as proficient in the English language will be enrolled. The scientific rationale for this is based on a lack of validated non-English language questionnaires suiting our study question. In addition, the Medication Assisted Therapy population at the Old Town Clinic site of Central City Concern has only English speaking drug and alcohol counseling groups (present in East-Side Clinic, not participating in our study), potentially creating bias if non-English speaking patients were enrolled at the Outside In site.

Consent will follow a clinic visit with a study provider, who will use a basic capacity assessment to determine eligibility to consent. This will include the following general principles of being able to understand, express a choice, appreciation, and reasoning.⁹

6. Procedures Involved

- The primary therapeutic intervention will be one tablet of Zepatier (elbasvir 50mg/grazoprevir 100mg) daily with or without food for 12 weeks. This dosage is consistent with current FDA approval for the treatment of hepatitis C.

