*Given the complexity of this population, the study pharmacist and clinicians will determine the most appropriate dispense frequency and method depending on the subjects' needs.

Visit 4 (week 2 of HCV treatment)

- Clinic Visit
- Compliance assessment
- Pharmacy dispenses another 2 weeks, or less if indicated, of HCV medication

Visit 5 (week 4 of HCV treatment)

- Clinic Visit
- Compliance assessment
- HCV RNA (if detectable, repeat HCV RNA in 6 weeks)
- Pharmacy dispenses 2 weeks, or less, if indicated, of HCV medication

Visit 6 (week 6 of HCV treatment)

- Clinic Visit
- Compliance assessment
- Recheck HCV RNA in those subjects who had detectable HCV RNA at week 4. If on repeat testing at week 6, viral load has increased by 10 fold $>1 \log_{10}$ IU/mL discontinue therapy. **Visit 7 (week 8 of HCV treatment)**

of HCV treatment)

- Clinic Visit
- Compliance assessment
- Check CMP. If liver enzymes >10 fold discontinue therapy

VISIT 8 (week 12 of HCV therapy) - End of Treatment

- Clinic Visit
- Compliance assessment

VISIT 9 (week 24) - 12 weeks after treatment completed

- Clinic visit
- HCV RNA to assess for SVR12, repeat genotype to clarify re-infection vs failure if +

VISIT 10 (week 60) - 48 weeks after treatment completed

- Clinic visit
- HCV RNA to assess for SVR48, repeat genotype to clarify re-infection vs failure if +
- Re-administer questionnaires

TOTAL DURATION - about 18 months

Quantitative Survey Data.

The following surveys will be performed and have been submitted for IRB approval:

- Chronic Illness Anticipated Stigma Scale (CIASS)
- MOS Social Support Survey
- SF-36 “Health and Well-Being” Survey

In addition, in-depth qualitative interviews will be performed Interviews will cover salient issues in participants’ lives at the community, organizational, household levels, as well as relationships (friends, family and sexual partners) perceived to influence study participation, treatment acceptability and adherence; risk taking behavior; and treatment preferences. By emphasizing the social and physical context of participant’s lives and their understandings of health, interviews are intended to provide insight into the ways in which these contexts shape treatment adherence and possible reinfection. The following constructs are constructs and sample themes that will guide in-depth interviews.

Level	Factors	Topics/Theme

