Subjects will be assigned a study ID on paper and data will be entered into an encrypted/password protected excel spreadsheet by the site principle investigator or study coordinator. The study ID will not contain any of the 18 HIPPA identifiers and will be available only to the PIs and IRB approved study collaborators. This document will be maintained, password protected, in the RED Cap repository. At each visit, a subject's study ID will be accessed from the Master List and a de-identified, study ID-linked opaque envelope with data sheets for all 10 visits will be pulled from a secure location. All non-clinical care data will be initially collected on paper by the data collector, provider, or study coordinator and then entered into de-identified data sets in the RED Cap repository by the study coordinator on a weekly basis. The paper copy will be replaced into the opaque envelope and then confirmed by a separate, IRB approved study volunteer. Standard of care clinical data will be entered in the electronic medical record and endpoints pre-specified in this protocol will be transferred to the RED Cap repository by the study coordinator on a weekly basis. When the study is fully enrolled and all participants complete the 48week visit, or are lost to follow up, the paper datasets will be destroyed in medical recycling facilities at each site.

In the retrospective OHSU cohort, all data will be entered immediately into RED Cap and then confirmed by a separate investigator at the OHSU site.

As part of the primary consent document, all participants will legally consent by written signature to storage of non-biological study data in a secure repository for future investigations. No biological specimens of any type will be stored beyond what is needed to complete laboratory tests at the point of care. For instance, blood will be drawn and sent to the clinical laboratory (LabCorp, Quest Diagnostics)

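### Visit 5 times the repeat of a detectable week-4 HCV RNA at week 10, but Visit 6 and its stopping rule need it at week 6

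*Combined protocol and SAP*

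**What the plan says.** The relevant text is the visit schedule under Treatment Scheme in Section 6 of the combined protocol and SAP.

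- At "Visit 5 (week 4 of HCV treatment") the laboratory line reads "HCV RNA (if detectable, repeat HCV RNA in 6 weeks").
- At "Visit 6 (week 6 of HCV treatment") the instruction is "Recheck HCV RNA in those subjects who had detectable HCV RNA at week 4". The stopping rule follows: "If on repeat testing at week 6, viral load has increased by 10 fold" (glossed as more than 1 log10 IU/mL), therapy is discontinued.
- Visit 7 (week 8) has a metabolic panel with a liver-enzyme stop. Visit 8 (week 12, end of treatment) has a clinic visit and a compliance assessment. Neither lists HCV RNA.

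The regimen, at the start of Section 6, is "one tablet of Zepatier (elbasvir 50mg/grazoprevir 100mg) daily with or without food for 12 weeks". Section 5d describes further contacts at both safety-net sites: "bi-weekly clinical pharmacist visits, monthly lab monitoring". Section 7c says that at each visit "data sheets for all 10 visits will be pulled from a secure location".

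**The concern.** The Visit 5 line gives an interval, not a visit label. An order placed at week 4 from that line would be booked for week 10, two weeks before treatment ends. The schedule has no visit there and says nothing about what to do with the result. The rule that would take a subject off a failing regimen is written for the week-6 result.

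Two things are at stake for an affected subject:

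- **The stopping rule.** The virologic stop could go unassessed at the time the protocol intends.
- **Secondary endpoints.** Treatment discontinuation and compliance with laboratory testing are both secondary endpoints (Section 4), and laboratory compliance is defined as the share of scheduled draws that were completed. For a subject detectable at week 4, the text does not settle whether the scheduled repeat is at week 6, week 10 or both.

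**Working it through.** The plan gives no figure to reproduce here. The check is schedule arithmetic.

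**Inputs (all from Section 6).** First on-treatment HCV RNA: week 4 (Visit 5). Interval to repeat as written: 6 weeks. Recheck and stopping rule: week 6 (Visit 6). Dose: one tablet daily for 12 weeks.

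**Timing of the repeat**

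| Source | Calculation | Treatment week | Numbered visit? | HCV RNA rule? |
|---|---|---|---|---|
| Visit 5 line | 4 + 6 | 10 | No | No |
| Visit 6 line | as stated | 6 | Yes | Yes |

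The numbered on-treatment visits are treatment start (week 0) and weeks 2, 4, 6, 8 and 12, so week 10 is not among them. The discrepancy is 10 − 6 = 4 weeks. An interval of 2 weeks would give 4 + 2 = week 6 and agree with Visit 6.

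**Other contacts.** The two-weekly pharmacist visits make a week-10 contact plausible, but no HCV RNA test or rule is attached to them.

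**Ceiling on extra treatment,** for a subject who would have met the week-6 rule but was not tested then:

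- Full course: 12 × 7 = 84 tablets.
- No rule applied at week 10, treatment completed: (12 − 6) × 7 = 42 tablets; 42/84 = 50% of the course.
- Provider stops on the week-10 result: (10 − 6) × 7 = 28 tablets; 28/84 = 33% of the course.

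Both figures assume that correct conduct would stop dosing on the day of the week-6 draw. Samples go to outside laboratories, so some delay for the result would occur anyway and the true excess would be somewhat smaller.

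**Number affected.** This would need the rate of detectable HCV RNA at week 4, the rate of a more than 10-fold rise by week 6, and the chance that staff overlook the Visit 6 instruction. The documents give none of these, so no count is offered.

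**The case against.** The strongest reply is that the schedule corrects itself. Visit 6 comes immediately after Visit 5, is specific, and agrees with its own stopping rule. The interval is most plausibly a slip for at week 6. Several features make a missed stop unlikely:

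- At Visit 5 the pharmacy dispenses no more than two weeks of drug, so a subject needs resupply at about week 6, when Visit 6 is due. Taking the extra tablets would require the subject to return for drug while staff omit the Visit 6 test.
- Section 5b puts monitoring during treatment under a medical provider panel, and the Section 4 definition of discontinuation allows a provider to stop therapy for safety.
- Data sheets are prepared for every visit.
- The separate data and safety monitoring plan is cited but is not in the supplied text, so it cannot be said that no other virologic rule exists anywhere.

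All of this stands as an argument about likelihood and weight. The tablet counts are ceilings for one subject, not a typical effect, and this is an inconsistency of wording rather than a deliberate choice of week 10. None of it reconciles the two lines. The supplied text has no rule saying which line prevails, and two sites with their own staff could read them differently. If both repeats were intended, the week-10 test would still have no visit and no action attached.

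**Conclusion.** The concern holds, as a minor point. The Visit 5 interval is wrong as written: it puts the repeat four weeks after the time at which Visit 6 and its stopping rule use it. The fault is confined to that one parenthesis.

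The per-subject ceiling is 42 of 84 tablets (50%), or 28 of 84 (33%) if therapy stops on the week-10 result. It rests on the subject being detectable at week 4, meeting the week-6 rule, being resupplied, and having the repeat booked from the Visit 5 line alone. That combination is unlikely, and its frequency cannot be estimated from the documents. No group-level effect on compliance or discontinuation can be computed. The timing of SVR12, the power statement and the week-8 liver-enzyme stop are unaffected. Confidence in the inconsistency itself is high, because both lines are current text and the arithmetic is direct.

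**What to change.** Change the Visit 5 parenthesis so that a detectable result is repeated at week 6 (Visit 6), and leave the Visit 6 stopping rule as it stands. The repeat, the numbered visit and the decision rule then coincide, and the scheduled draw for laboratory compliance is unambiguous. The cost is a one-line protocol correction, with no added visit, test or change in sample size.

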Project Title:

Hepatitis C Treatment in PWIDs: MAT or Syringe Exchange Assisted-therapy vs Standard of Care

NCT Number:

NCT03093415

Last Review/Edits:

January 20, 2019

Protocol 1. Protocol Title

Hepatitis C Treatment in PWIDs: MAT or Syringe Exchange Assisted-therapy vs Standard of Care

IRB 16357

2. Objectives/Hypothesis

Hypothesis: Treatment adherence and hepatitis C (HCV) infection cure rates using a simple 1-pill a day regimen of a direct anti-viral agent (DAA) in two unique care delivery models for marginalized persons with HCV infection, Outside In needle exchange program serving people who inject drugs (PWID) and Old Town Clinic, an integrated multi-disciplinary primary care clinic serving homeless and low income adults, will be similar to HCV patients treated in a traditional Hepatology Clinic at an Academic Health Center

Purpose: Determine if two unique safety net clinics (intervention group) with comprehensive behavioral health, pharmacy and medical services will improve HCV therapy adherence and reduce re-infection rates such that overall cure rates will be maintained and be similar to cure rates seen over the same time period in a traditional hepatology clinic setting (comparison group). The expectation is that these safety net clinics with comprehensive healthcare services should normalize the chaotic lifestyles of the patients that typically utilize safety net clinics.

Goal: If this study can demonstrate that such well-established comprehensive multidisciplinary safety net clinics that see an extremely marginalized population that are typically excluded from access to HCV therapies can achieve similar HCV treatment responses as seen in traditional clinics, the use of such sites as HCV treatment centers can be utilized on a national scale.

AIMS:

1. Identify clients/subjects in each care setting with genotype 1 or 4 HCV infection ≥ 18 years of age that wish to be treated.
 - a. Outside In Injection Drug Users Health Services (n=25)
 - b. Old Town Clinic (n=25)
 - c. Retrospective cohort of subjects at Oregon Health & Science University Hepatology Clinic (n=50)
2. Prior to treatment each client/subject is administered a questionnaire assessing motivation, readiness for treatment
3. Assess adherence to treatment regimen, laboratory testing, discontinuation rates, cure rates, and reinfection rates 1 year post treatment

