The results of this study will give insight into the feasibility of using safety net medical sites such as needle exchange programs and community health centers serving low income or homeless populations to safely and effectively treat this vulnerable population that is disproportionately affected by HCV infection. Furthermore, feedback from clients/patients using validated questionnaires could identify modifiable barriers to treatment success. Findings from this study could help expand the HCV treatment capacity beyond subspecialty practice and even the traditional primary care clinic.

4. Study Design

Study Objectives

Primary Objective: Determine if the clinical effectiveness of Zepatier in treating patients with HCV infection and mild fibrosis in two safety net sites, which offer comprehensive services to normalize the chaotic lifestyles of people who inject drugs and the homeless, is similar to what is expected in a tertiary hepatology clinic that cares for a more traditional patient population.

Secondary Objective: Identify client/patient factors that impact HCV treatment success in this population

Study Endpoints

Primary Endpoint

- Sustained virologic response rates measured at 12 weeks post treatment (SVR12)-Intention to Treat analysis (taking into account treatment discontinuation and failure rates)
- Persistently HCV infection free after 48 weeks of treatment cessation (SVR48)

Secondary Endpoints

- Adherence determined by client/subject self-reported medication adherence measured by percentage of pills taken on a monthly basis, as well as compliance with laboratory testing

- Treatment discontinuation rates including loss to follow up
- Percent of genotype 1a patients with baseline NS5A resistance

Relapse with substance use disorder in Old Town Clinic setting

Exploratory analysis of potential client/subject factors impacting readiness for treatment, non-adherence, or reinfection based on questionnaires administered at baseline and at 48 weeks post treatment

Study Design

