All data will be collected by the primary provider, site principle investigators, or site coordinators. This data will be disassociated with personal identifiers, re-associated with a nondescript study ID, and uploaded into OHSU-sanctioned confidential data management service such as RED Cap, on a daily basis.

We will collect basic demographical information, including age, gender, ethnicity, substance abuse disorder/drug of choice and current use status, and housing status. The primary outcome measured will be SVR at 24 weeks (12 weeks post-treatment). Secondary outcomes include adherence (% pills missed, per fill and total), relapse or ongoing injection drug use at 48 weeks, and re-infection or treatment failure at 48 weeks.

Data storage will be for a period of 5 years or less, unless formal permission requested of the OHSU IRB for extension. Subjects will be consented for indefinite data storage.

Please see uploaded data collection and consent forms.

b. Sharing of Results with Subjects

All personal, clinical information will be shared with subjects in accordance of the standard of care. This includes lab values (done at CLIA certified laboratories Quest and Labcorps), imaging results, and other aspects of routine hepatitis C treatment. Results of secondary measures, including survey data and indepth interviews, will not be shared directly with subjects. Subjects will be able to access the final publication(s) upon request.

c. Data and Specimen Banking

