After study completion, any future release of data collected will be contingent upon the repository guardian verifying a separate full IRB approval for each specific human subject research activity that uses identifiable repository data. The repository guardian will be personally responsible for verifying that future releases of data are done in concordance with pre-proposed limits and the original consent. Data transport at the time of any potential future IRB approved data sharing will be clarified and approved at the time of data by submission of an updated Repository Sharing Agreement and separate IRB approval. Any updated data requests and Repository Sharing Agreements will be stored alongside study data in the Red Cap repository in a separate file entitled "Repository Sharing Agreements and External Data Requests." This will be maintained and tracked by [name]. External researchers will be required to use the Red Cap repository for all data storage, therefore data transfer will not be necessary and data security ensured.

No data submittal from outside sources is expected.

8. Data Analysis

- 1) For primary endpoint: descriptive analysis and chi-squared test for comparative analysis
- 2) For secondary endpoints:
 - Descriptive analysis
 - Explore bivariate and multivariate associations between psychosocial factors computed through scales (e.g., stigma, social support, quality of life) and (a) treatment readiness at baseline, (b) treatment outcomes [SRV, biological outcomes, etc.] at 12 months, (c) re-infection (or SRV) at 48 months. Demographic controls will include age, education, work status, and relationship status.
 - Conduct constant comparative qualitative analysis of focus group and individual discussions using Atlas.ti software. The domains of analysis will include lived experiences with stigma, discrimination, positive and negative social support systems, and risk management. Emergent themes and domains identified through qualitative analysis will result in a richer understanding of factors that contribute to implementing successful treatment for people who currently use drugs.

In addition to the above, mixed methods data will comprise biological data, psychosocial data collected via questionnaires, and qualitative narrative data from transcribed in-depth interviews.

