Analytic across-case analysis entails comparative analysis, distinguishing between groups of people who exhibit different behavioral patterns. This allows the investigators to go beyond simple assertions about majority and minority patterns and to make analytic—as opposed to descriptive—statements about how certain values or behaviors relate to broader psychosocial and institutional factors.

Power/Sample Size:

Based upon a sample size of n=50 subjects in the combined safety net/needle exchange clinics and 50 subjects in the retrospective comparator group, this study has 80% power to detect a 20% difference between groups; this calculation is based on the assumption that the retrospective comparator group will have and SVR12 rate of 95% (taking into account treatment discontinuation and relapse rates, i.e. intention to treat analysis) compared to SVR12 rate of 70% in the safety net clinic patients.

In the intervention group (safety net clinics) a total of 50 subjects will be enrolled to allow for a 10% attrition and loss to follow up.

9. Privacy, Confidentiality, and Data Security

All data will be collected and entered in a private, clinical care environment, behind closed doors. All study collaborators with access to personal data, de-identified or not, will be required to undergo full OHSU IRB training.

At Old Town Clinic, subjects will be recruited as described in Section 5e. There will be limited risk of a privacy violation with this method. The consent process will be performed during the course of a clinical visit, in an exam room, one-on-one with the site coordinator.

At Outside In, subjects will be recruited as described in Section 5e. There will be limited risk of a privacy violation with this method. The consent process will be performed after a clinical visit in a private office in the syringe exchange, one-on-one with the site coordinator.

At all sites, laboratory and/or imaging tests, clinical visits, dispensation of medications, and communication of test results will be performed in concordance with HIPPA appropriate clinical care. All surveys and qualitative data will be collected in a private space, such as an exam room or meeting room behind closed door.

For more details, please see section 7c above.

10. Provisions to Monitor the Data to Ensure the Safety of Subjects

See DSMP document, attached.

9. Risks and Benefits a. Risks to Subjects

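### The primary question is whether safety-net cure rates are similar to the hepatology clinic's, but no criterion for similar is set and the only comparative analysis is a chi-squared test of difference

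*Combined protocol and SAP*

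**What the plan says.** Similarity is the question throughout. In Section 2 the hypothesis is that adherence and cure rates "will be similar to HCV patients treated in a traditional Hepatology Clinic at an Academic Health Center". The goal in the same section makes national use of such sites conditional on showing that they "can achieve similar HCV treatment responses as seen in traditional clinics". The primary objective in Section 4 asks whether effectiveness "is similar to what is expected in a tertiary hepatology clinic that cares for a more traditional patient population".

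The comparison, in Section 4 under Study Design, is the overall SVR12 of the prospective safety-net patients (25 at each of two sites) against SVR12 in 50 retrospective OHSU patients. The analysis in Section 8 is "For primary endpoint: descriptive analysis and chi-squared test for comparative analysis". The Power/Sample Size paragraph is framed as detection of a difference: "this study has 80% power to detect a 20% difference between groups", with a comparator SVR12 of 95% "compared to SVR12 rate of 70% in the safety net clinic patients".

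The primary endpoint list in Section 4 also includes "Persistently HCV infection free after 48 weeks of treatment cessation (SVR48"), whereas Section 7 says "The primary outcome measured will be SVR at 24 weeks (12 weeks post-treatment"). No criterion for similar is given for either endpoint.

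**The concern.** A chi-squared test takes equality as its null hypothesis. Rejecting it is evidence of a difference. Failing to reject it may mean that the rates are close, or only that 100 patients were too few to separate them. The plan sets no margin, no equivalence or non-inferiority hypothesis and no interval rule, so nothing says in advance which results would count as similar.

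The Power/Sample Size paragraph does not fill the gap. A detectable difference is not a margin of acceptable loss, and this one is not even a single number: the text says 20%, but 95% against 70% is 25 points.

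At stake is the study's declared use. A finding of similar responses is meant to support these sites as treatment centres nationally. Without a rule, the reading of a non-significant result would be chosen after the data are seen, and a real loss of cure could be reported as similarity.

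**Working it through.** **Inputs.** From the Power/Sample Size paragraph: 50 against 50, comparator SVR12 95%, safety-net SVR12 70%, a 20% difference, 80% power. From Section 9 (Potential Benefits to Subjects): drug efficacy of 92% to 97%. Not in the documents and assumed here: two-sided alpha of 0.05, and Pearson chi-squared without continuity correction unless stated.

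**1. The plan's own figure.** For a two-proportion test of difference, with p̄ the mean of the two rates,

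power = Φ{ [ |p1 - p2|·√n - 1.96·√(2p̄(1 - p̄)) ] / √( p1(1 - p1) + p2(1 - p2) ) }.

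- 95% vs 75% (20 points): (1.414 - 0.990) / 0.485 = 0.876, power 80.9%.
- 95% vs 70% (25 points): (1.768 - 1.053) / 0.507 = 1.408, power 92.1%.

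The stated 80% matches the 20-point reading. Either way it is the power of a test of difference.

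**2. How often that test is non-significant.** Let X ~ Bin(50, safety-net rate) and Y ~ Bin(50, comparator rate). Sum the joint probability over all pairs with p ≥ 0.05.

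| True comparator | True safety-net | Non-significant | With Yates correction |
|---|---|---|---|
| 95% | 90% | 86% | 94% |
| 95% | 85% | 61% | 76% |
| 95% | 80% | 34% | 49% |
| 95% | 75% | 15% | 25% |
| 95% | 70% | 5% | 10% |
| 92% | 82% | 67% | 79% |
| 97% | 87% | 54% | 72% |

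Across the 92% to 97% range, a true 10-point shortfall is therefore more likely than not to give a non-significant result.

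**3. What those non-significant results leave open.** At 95% vs 85%, 50% of all trials are non-significant and also have a 95% Newcombe interval reaching a shortfall of 15 points or worse. In 28% of all trials the interval reaches 20 points or worse.

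**4. One data set.** OHSU 47/50 (94%), safety-net 41/50 (82%).

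- χ² = 100·(41·3 - 9·47)² / (88·12·50·50) = 9,000,000 / 2,640,000 = 3.41, p = 0.065.
- Difference = 0.82 - 0.94 = -0.12. Wilson limits: 0.692 to 0.902 (safety-net) and 0.838 to 0.979 (OHSU).
- Newcombe lower limit: -0.12 - √[(0.82 - 0.692)² + (0.979 - 0.94)²] = -0.254.
- Newcombe upper limit: -0.12 + √[(0.902 - 0.82)² + (0.94 - 0.838)²] = +0.011.

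The test shows no significant difference, while the data allow a 25-point loss of cure.

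**5. What an interval rule would do at 50 vs 50.** This is the probability that the Newcombe lower bound lies above minus the margin, with the comparator at 95%. The margins are illustrations only, because the documents give none.

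| Margin | True safety-net 95% | True safety-net 90% |
|---|---|---|
| 10 points | 51% | 13% |
| 15 points | 82% | 37% |
| 20 points | 97% | 71% |

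When the true shortfall equals the margin, the rule wrongly passes in 2.2%, 2.2% and 2.5% of trials. Whether 50 per group is enough thus depends on a margin that the plan does not state.

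**The case against.** The strongest reply is that this is a small study, called a pilot in Section 5f, with a non-randomised retrospective comparator and a descriptive analysis listed ahead of the test. On that reading, similar is a loose descriptive word. The protocol also never says that p > 0.05 will be taken as similarity, and the test does work as a screen for a large loss: on the uncorrected figures it misses a fall to 70% in only 5% of trials.

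Parts of this stand. The misreading is a risk and not a stated intention, and the test and power statement are coherent with each other as a search for a large deficit. But a screen for a 20- or 25-point loss does not answer whether rates are similar. The pilot label does not remove the formal hypothesis, the power calculation or the national-scale goal, and no interval or decision is attached to the descriptive analysis.

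Two narrower points are fair. The figures depend on the version of the test, which Section 8 does not name; the Yates column shows that correction strengthens the concern. For SVR48, Aims 3 and 4 imply a one-year comparison across the three sites, but no section says that 48-week HCV RNA results will be available for the retrospective patients.

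**Conclusion.** The concern holds, and the primary analysis is wrong as written: carried out exactly, it cannot support the conclusion that the study is designed to reach. The absence of any criterion for similar is a matter of text and needs no assumption. The size rests on 50 per group, two-sided 5% and an uncorrected test. Under these, a true 10-point shortfall is non-significant in 54% to 67% of trials (72% to 79% with Yates correction), and a 5-point shortfall from 95% in 86%. This should be corrected before the analysis. SVR48 has the same gap for as long as it is listed as primary.

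**What to change.** In Section 8:

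- Make the primary analysis the difference in SVR12, safety-net minus OHSU, with a two-sided 95% Newcombe or Miettinen-Nurminen confidence interval. Do the same for SVR48 if it stays primary.
- State that p > 0.05 is not evidence of similarity, and keep the chi-squared test as descriptive.
- By default, report the difference and interval and leave similar out of the conclusion.
- Allow the claim only if the lower bound lies above a margin that the sponsor justifies on acceptable loss of cure and states before analysis. This treats the question as one of not losing cure. If two-sided equivalence is meant, the plan should say so and apply the rule to both bounds.

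**Cost.** For SVR12 this is protocol wording, with no extra patients or data, plus the work of justifying a margin if the claim is wanted. For SVR48 it also needs 48-week results from the OHSU cohort. The claim becomes harder to make: with true rates of 95% and 90%, a 15-point rule fails in 63% of trials (100 - 37) and a 20-point rule in 29% (100 - 71). An interval rule does not remove confounding from the retrospective comparator.
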